3.2.3.2. Treatment-emergent Adverse Event (TEAE)

Any event reported on the eCRF that occurs on or after the initiation of IMP until the end of AE reporting period per protocol is considered treatment emergent.

Additionally, it is assumed that an Adverse Event which was reported to have started on Day 1 without an associated onset time is assumed to be treatment emergent.

3.2.4. Clinical Safety Laboratory Assessments

The clinical laboratory tests as listed in the protocol will be performed in accordance with the laboratory manual and the Schedule of Assessments. All results, including repeats, will be included in the laboratory reports. The investigator must review the laboratory report, document this review, and record any clinically relevant changes occurring during the trial in the AE section of the eCRF.

3.2.4.1. Treatment-emergent Laboratory Abnormality and Toxicity

A treatment-emergent laboratory abnormality is defined as value outside the normal range which occurs on or after the start of IMP and up to the last contact following discontinuation of IMP.

A treatment-emergent laboratory toxicity is defined as an increase of at least one abnormality severity grade (specifications in [Section 9.8](#)) from the baseline assessment at any post baseline visit which occurs after the first administration of IMP and through last test results of the study. If a laboratory assessment obtained on Day 1 with unknown collection times will be assumed to be an assessment prior to the initiation of IMP. If the relevant baseline assessments are missing for a given subject, any post-baseline severity grade at 1 or more is considered a treatment-emergent laboratory toxicity.

3.2.5. Columbia-Suicide Severity Rating Scale (C-SSRS)

Suicidality will be monitored during the trial using the C-SSRS. It was designed to quantify the severity of suicidal ideation and behavior.

This trial will use the “Baseline/Screening” and “Since Last Visit” versions of the scale. The “Baseline/Screening” version, which assesses the lifetime experience of the subject with suicide events and suicidal ideation and the occurrence of suicide events or ideation within a specified time period prior to entry into the trial, will be completed for all subjects at screening to determine eligibility and confirmed at baseline. Any subject with active suicidal ideation or suicidal behaviors within the last 6 months, suicidal behaviors within the last 2 years, or who in the clinical judgment of the investigator presents a serious risk of suicide should be excluded from the trial.

The “Since Last Visit” C-SSRS form will be completed at all visits after screening and baseline. The investigator will review the results of the “Since Last Visit” C-SSRS during the trial to determine whether it is safe for the subject to continue in the trial. If a subject demonstrates potential suicidal ideation associated with actual intent or method or plan as indicated by “YES” answers on item 4 or 5 of the C-SSRS, the investigator will evaluate whether a risk assessment by a qualified mental health professional (or the investigator alone if the investigator is a qualified mental health professional) is needed and whether the subject should continue in or be discontinued from the trial.

Details of C-SSR categories as well as definition of treatment emerging events are provided in [Section 9.3](#).

3.2.6. Vital Signs

Vital signs include systolic and diastolic blood pressures, heart rate, and body temperature. Duplicate measurements of blood pressure and heart rate will be obtained supine (after 5 minutes of rest) and 1 measurement of blood pressure and heart rate will be obtained on standing (2 minutes after rising from supine to standing). The duplicate values will be individually recorded, and the values will be averaged by the sponsor for the time point assessment. Body temperature will be obtained once, at the time of the first blood pressure measurement.

3.2.7. Electrocardiograms

Single or triplicate 12 lead ECGs will be obtained during the trial. All ECG recordings be obtained after the subject has been supine and at rest for at least 5 minutes. A triplicate set of ECGs is 3 consecutive ECGs collected 1 to 2 minutes apart over a 5 minute period.

A single ECG will be obtained at the Screening Visit. For US sites, three sets of triplicate ECGs will be obtained during the 45 minutes before administration of the first dose of IMP on Day 1 (at -45, -30, and -15 minutes), and a single set of triplicate ECGs will be obtained ~1 hour after administration of the first dose of IMP on Day 1, just prior to the time of collection of the PK blood sample. One set of triplicate ECGs will be obtained at the Weeks 5, 11, 14, 22, and 27 clinic visits, just prior to the time of collection of the PK blood sample. The triplicate ECG information from US sites will be used in a C-QT analysis with results reported separately. For non-US sites, one set of triplicate ECGs will be obtained before administration of the first dose of IMP on Day 1, and a single ECG will be obtained ~1 hour after administration of the first dose of IMP on Day 1, just prior to the time of collection of the PK blood sample. Single ECGs will be obtained at the Weeks 5, 11, 14, 22, and 27 clinic visits, just prior to the time of collection of the PK blood sample. A central ECG service will be used for reading all ECGs to standardize interpretations for the safety analysis.

[figure not shown]
3.2.8. Prior Medications, Concomitant Medications and Medications Taken Post Last Dose of IMP

Prior medications are those medications taken prior and ended prior to the initiation of IMP. These medications will be captured in the CONCOMITANT MEDICATIONS eCRF.

Concomitant medications are those medications taken on or after the initiation of IMP. These medications include those medications started before the initiation of IMP and continuing post Day 1. Medications that start after the last dose of IMP until the end of protocol-specified reporting period will be classified as taken post last dose and will not be considered concomitant. These medications will be recorded in the eCRF. The investigator will record all medications and therapies (including vaccines, over-the-counter or prescription medicines, vitamins, and/or herbal supplements) that are used by the subject from 30 days before the informed consent form (ICF) is signed through the end of the Safety Follow-up Period (Week 31 or early termination). The investigator will also record all medications and therapies taken or received by a subject for treatment of an AE or that cause an AE through Week 31 or early termination.

3.2.9. Physical and Neurological Examinations

A complete physical and neurological examinations will be conducted at screening and at the end of treatment visit (Visit 11 or early termination visit). Any condition present post-baseline physical or neurological examination that was not present at the baseline examination should be documented as an AE and followed to a satisfactory conclusion.

3.3. Pharmacokinetics

Blood samples for measurement of plasma concentrations of tavapadon and CVL-0000053, its major metabolite, will be collected ~1 hour after administration of the first dose of IMP on Day 1 and at the clinic visits at the end of Weeks 5, 11, 14, 22, and 27.

Drug concentration information will not be reported to investigative sites, clinical database or any blinded study personnel until the trial has been completed and unblinded.

4. DATA CONVENTIONS AND VISIT WINDOWS

4.1. Data Conventions

4.1.1. Age

Age is the age at the time of informed consent and is as captured on the eCRF (note: date of birth is not captured on the eCRF).

4.1.2. Day 1

Day 1 is the day IMP is first initiated.

4.1.3. Endpoint

Endpoint as defined as the primary time point for the efficacy assessments is Week 26.

4.1.4. Study Day of an Event

Study day of an event is defined relative to Day 1 as:

Study Day = event date – date of Day 1 (+ 1, if event date \geq date of Day 1).

This calculation will result in negative study days for an event occurring prior to the start of IMP and positive study days for an event on or after the start of IMP. There will be no Day 0 value to match the schedule of events.

4.1.5. Days on Study

Days on Study is the number of days from Day 1 to the date of study completion or early termination as recorded on the END OF STUDY eCRF.

4.1.6. Days on IMP

Days on IMP is the number of days from Day 1 to the date of last dose of IMP as recorded on the EXPOSURE eCRF.

4.1.7. Baseline Value

For purposes of analysis, the baseline value of a given assessment is defined as the last value obtained prior to initiation of IMP. Should the Day 1 visit value be obtained after the first dose of IMP or if this value is not available at Day 1, the most recent value obtained prior to the first dose of IMP will be used for the baseline value.

For US subjects with triplicate ECGs taken at 3 pre-dose timepoints, the baseline value will be defined as the average of the available pre-dose ECG values (i.e. triplicate ECGs at -45 minutes pre-dose, -30 minutes pre-dose, and -15 minutes pre-dose). For non-US subjects, the baseline value will be defined as the average of the available pre-dose ECG values. Scheduled records will be selected over unscheduled records if a tie breaker is needed.

For blood pressure and heart rate measurements, baseline is defined as the average of the duplicates at the last visit prior to the IMP administration. If no duplicate is available, the last non-missing value prior to the initiation of IMP will be used.

4.1.8. Change from Baseline

Change from baseline for a given variable is defined as the value on a given Study Day (Time Point) minus the Baseline Value.

4.1.9. Orthostatic Change

Orthostatic change is calculated as the difference in the standing value from the supine value (i.e., supine value – standing value). If an average value is available at a given visit and date, it will be used for the calculation of orthostatic change. If an average value is not available, the individual record obtained on a given visit and date will be used.

4.1.10. Duration of Titration Phase

The duration of the titration phase will be calculated as the days in [REDACTED] of the dosing schedule.

4.1.11. Duration of Maintenance Phase

The duration of the maintenance phase will be calculated as the days in [REDACTED] of the dosing schedule.

4.1.12. Average Dose of Titration Phase

The average dose of the titration phase will be calculated as the sum of the milligrams of study drug taken in [REDACTED] of the dosing schedule divided by the duration of days in the titration phase.

4.1.13. Average Dose of Maintenance Phase

The average dose of the maintenance phase will be calculated as the sum of the milligrams of study drug taken in [REDACTED] of the dosing schedule divided by the duration of days in the maintenance phase.

4.1.14. Compliance with Study Drug

Accountability and compliance will be assessed through self-reporting by the subject and by tablet count at each clinic visit. For analysis purposes, evaluation of compliance will be based on the site assessment of compliance as recorded on the DRUG ACCOUNTABILITY eCRF. Compliance will be calculated as a percentage based on the total number of tablets taken relative to the total expected number of tablets based on days on study. If a kit was lost and return information was available, the return information will be used for the compliance calculation. If a kit was lost and no return information was available, it is assumed that the tablets were not taken for the compliance calculation. If return information is not available and the kit was not lost, it is assumed that the tablets were taken for the compliance calculation.

If a kit was redispensed and the number of tablets redispensed is not available, it is assumed that the number of tablets that were partially returned were redispensed for the compliance calculation.

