Prolactin level		X ^u									X ^u		
Serology (HIV, HbsAg, and HCV)	X												

Table 2 Schedule of Assessments

Trial Period:	Screen	Baseline	Treatment									Safety Follow-up ^a
Trial Week:	-4 to -1	1	2	5	8	11	14	18	22	26	27 ^b	31
Trial Day:	-31 to -1	1	14±3	35±3	56±3	77±3	98±3	126±3	154±3	182±3	189±3	217±3
Visit/Contact:	Visit 1	Visit 2	Visit 3	Visit 4	Visit 5	Visit 6	Visit 7	Visit 8	Visit 9	Visit 10	Visit 11 (EOT/ET)	Telephone ^c
Dipstick urinalysis ^o	X	X				X			X		X	
Serum pregnancy test ^p	X											
Urine dipstick pregnancy test ^p		←-----→										
Urine drug screen ^q	X	←-----→									X	
Plasma PK sample ^r		X		X		X	X		X		X	
Future biospecimen research blood sample ^s		X										
IMP Administration and Compliance^t												
Dispense IMP		X	X	X	X	X	X	X	X	X		
Assess IMP compliance			X	X	X	X	X	X	X	X	X	

Abbreviations: ADL = activities of daily living, CGI-I = Clinical Global Impression – Improvement, CGI-S = Clinical Global Impression – Severity of Illness, C-SSRS = Columbia-Suicide Severity Rating Scale, ECG = electrocardiogram, eCRF = electronic case report form, EQ-5D-5L = EuroQol 5 Dimension 5 Level, ESS = Epworth Sleepiness Scale, EOT = end of treatment, ET = early termination, HbsAg = hepatitis B surface antigen, HCV = hepatitis C virus, HIV = human immunodeficiency virus, IMP = investigational medicinal product, [REDACTED], MDS-UPDRS = Movement Disorder Society – Unified Parkinson’s Disease Rating Scale, MoCA = Montreal Cognitive Assessment, PDQ-39 = 39-Item Parkinson’s Disease Questionnaire, PGIC = Patient Global Impression of Change, PK = pharmacokinetic, QUIP-RS = Questionnaire for Impulsive-Compulsive Disorders in Parkinson’s Disease-Rating Scale.

- Subjects who prematurely discontinue from the trial or who are not eligible for or choose not to participate in the open-label extension trial (Protocol CVL-751-PD-004) are to participate in the 4-week Safety Follow-Up Period. Subjects who proceed into the open-label extension trial will go directly into that trial and will not complete the Safety Follow-Up Period.
- The assessments scheduled for the Week 27 visit are to be performed for any subject who prematurely discontinues from the trial.
- Contact with subjects via telephone call or other means of communication to check on their status.
- Informed consent must be obtained before any trial-related procedures are performed.

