6.4 Trial Treatment Compliance

All IMP will be dispensed by responsible trial personnel. Subjects will be counseled on the importance of taking the IMP as directed (once daily in the morning, with or without food) at each clinic visit and will be instructed to bring all used and unused blister cards to each clinic visit. Accountability and compliance (as assessed through self-reporting by the subject and by tablet count at each clinic visit) will be documented in the subject's

trial records. Deviation(s) from the prescribed dosage regimen should be recorded in the eCRF.

If poor compliance is encountered (eg, multiple missed doses resulting in <80% overall compliance at any point in the trial), discontinuation of the subject from the trial should be considered. Subjects who habitually miss visits or habitually attend visits outside of the protocol-defined visit window are also defined as noncompliant and should be considered for discontinuation. The medical monitor should be contacted if the investigator is uncertain whether a subject's lack of compliance merits discontinuation from the trial.

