7.3 Individual Subject Discontinuation

After treatment assignment, a subject may stop treatment permanently for a variety of reasons. Treatment discontinuation may be initiated by a subject who is not satisfied with treatment or may become medically necessary due to AEs, required treatment with a disallowed medication or therapy, or other issues, as determined by the investigator.

A subject may discontinue the IMP for any of the following reasons:

- Adverse event
- Death
- Worsening of PD symptoms to such an extent that, in the judgment of the investigator, the subject requires additional anti-PD medications
- Treatment with prohibited concomitant medications
- Noncompliance with the study schedule
- Noncompliance with the study drug
- Withdrawal by subject
- Pregnancy
- Physician decision

If a subject discontinues the IMP due to an AE, the investigator or other trial personnel will make every effort to follow the event until it has resolved or stabilized.

All subjects have the right to withdraw consent for further participation in the trial at any time without prejudice. Subjects cannot withdraw consent for use of data that have already been collected as part of the trial but can withdraw consent for future

participation. The investigator can also discontinue a subject from the trial at any time if medically necessary. Unless the subject provides written withdrawal of consent or there is other written documentation by the investigator confirming the subject's verbal intent to completely withdraw from the trial, subjects should be followed for all protocol-specified evaluations and assessments, if possible.

Complete withdrawal of consent requires a subject to refuse of ALL of the following methods of follow-up:

- Participation in all follow-up procedures specified in the protocol (whether in-clinic or by telephone)
- Participation in a subset of protocol specified follow-up procedures (by a frequency schedule and method, as agreed by subject and staff)
- Contact of the subject by trial personnel, even if only by telephone, to assess current medical condition, and obtain necessary medical or laboratory reports relevant to the trial's objectives
- Contact of an alternative person(s) who has been designated in source records as being available to discuss the subject's medical condition, even if only by telephone, mail, or e-mail (eg, family, spouse, partner, legal representative [as defined per local regulations], friend, neighbor, or physician)

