1.3.2. Blinding

The tavapadon and placebo tablets will be identical in appearance and will be packaged in identically appearing blister cards. All subjects will take 3 tablets once daily of IMP throughout the Treatment Period, either all tavapadon tablets, all placebo tablets, or a combination of tavapadon and placebo tablets. Tablets will be packaged to allow dosage adjustments to be made without breaking the trial blind.

Treatment assignments will be blinded to the investigators and other trial site personnel, the subjects, and all sponsor personnel who are involved in the conduct of the trial (including trial monitoring, data management, and data analysis). Access to the treatment codes will be restricted to personnel who are responsible for generating and maintaining the randomization code, packaging the IMPs, operating the IVRS/IWRS, analyzing the PK blood samples, or reporting serious adverse events (SAEs) or adverse events of special interest (AESI) to regulatory agencies.

Documentation of breaking the blind should be recorded in the subject's medical record and eCRFs, with the reason for breaking the blind, the date and time the blind was broken, and the names of the personnel involved. Once the blind is broken for a subject, treatment with the IMP may not be reinitiated for that subject.

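### SAP 4.1.14 counts expected tablets over days on study, not days on IMP, so compliance can be understated for subjects who stop treatment before their end-of-study date

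*SAP*

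**What the plan says.** SAP 4.1.14 expresses compliance as the percentage of tablets taken "relative to the total expected number of tablets based on days on study". SAP 1.3.2 fixes the daily count: "All subjects will take 3 tablets once daily of IMP throughout the Treatment Period".

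The SAP defines two durations, taken from two different eCRF pages:

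- SAP 4.1.5, from the end-of-study page: "Days on Study is the number of days from Day 1 to the date of study completion or early termination".
- SAP 4.1.6, from the exposure page: "Days on IMP is the number of days from Day 1 to the date of last dose of IMP".

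The protocol separates stopping IMP from leaving the trial. Protocol 7.3 says that, short of documented complete withdrawal, "subjects should be followed for all protocol-specified evaluations and assessments, if possible". Under the Schedule of Assessments (Protocol 1.3), subjects who discontinue from the trial prematurely have the Week 27 assessments and "are to participate in the 4-week Safety Follow-Up Period". Protocol 4.4 treats a subject as a completer once the Week 27 visit is done.

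SAP 5.8 summarises compliance by treatment group in the FAS, next to days on study drug and reasons for stopping IMP.

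**The concern.** No tablets are due once IMP has been stopped for good. A denominator that runs past the last dose therefore treats off-drug days as missed doses, and a subject who took every tablet until stopping can score below 100%. Completers are dosed up to about the Week 27 visit, where their participation is complete, so they carry little or no off-drug time. Any bias falls mainly on early stoppers, always lowers the figure, and grows with an arm's dropout.

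What is at stake is the meaning of one descriptive number. Readers use compliance by arm to judge whether the assigned treatment was taken while it was prescribed. Under this definition it also carries some of the dropout, which SAP 5.8 already reports separately.

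**Working it through.** The documents state no compliance figure, so there is none to reproduce. The check is a direct ratio.

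**Inputs**

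- Tablets per day: 3 (SAP 1.3.2).
- I = days on IMP (SAP 4.1.6).
- g = days from last dose to the end-of-study date. Not in the documents; range taken as 0 to 28. The top of the range is the 4-week safety follow-up.
- Stopping day: not in the documents; Day 60 for the main illustration, Days 41 and 126 for comparison.
- Dropout: the only figure in the documents is the overall 27% in the sample size sections (Protocol 9.2, SAP 1.2). Values of 15% and 40%, and a 20-point difference between arms, are assumptions.

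**One fully adherent subject**

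Score = 3I / [3(I + g)] = I / (I + g)

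| Stop | g = 0 | g = 7 | g = 14 | g = 28 |
|---|---|---|---|---|
| Day 41 | 100% | 85.4% | 74.5% | 59.4% |
| Day 60 | 100% | 60/67 = 89.6% | 60/74 = 81.1% | 60/88 = 68.2% |
| Day 126 | 100% | 94.7% | 90.0% | 81.8% |

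**Arm mean**

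With completers at 100% and every dropout stopping on Day 60, the mean is (1 − d) × 100% + d × I/(I + g), where d is the dropout proportion:

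| Dropout | g = 0 | g = 7 | g = 14 | g = 28 |
|---|---|---|---|---|
| 15% | 100 | 98.4 | 97.2 | 95.2 |
| 27% | 100 | 97.2 | 94.9 | 91.4 |
| 40% | 100 | 95.8 | 92.4 | 87.3 |

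**Difference between two arms whose dropout differs by 20 points**

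Difference = 0.20 × [100 − score at Day 60]:

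- g = 0: 0 points
- g = 7: 0.20 × 10.4 = 2.1 points
- g = 14: 0.20 × 18.9 = 3.8 points
- g = 28: 0.20 × 31.8 = 6.4 points

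**With days on IMP as the denominator**

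The score is I/I = 100% for every subject who took all tablets until stopping, whatever the gap or the arm's dropout.

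**The case against.** The strongest reply is that the gap may be small or absent. Days on study stop at early termination, so an early leaver is not charged tablets up to Week 27. If the end-of-study date equals the last-dose date, there is no bias. The schedule labels Visit 11 as the end-of-treatment or early-termination visit, and completion is tied to the Week 27 visit. Protocol 4.1.2 also discontinues subjects who cannot tolerate certain doses from the trial, not just from IMP. No section says that the end-of-study date is the follow-up call. All of this stands: the 28-day column is an upper scenario and the less supported reading. It does not remove the point, because Protocol 7.3 asks for continued follow-up after IMP stops and the SAP does not say how the end-of-study date is set for those subjects.

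The 6-point difference also depends on dating dropouts to the call and completers to Week 27. If the call dated everyone and no completer entered the extension, completers would score 189/217 = 87.1%. The difference would then shrink to 0.20 × (87.1 − 68.2) = 3.8 points.

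A further reply is that days on study catches a subject who quietly stops tablets weeks before the termination visit, which is real non-adherence. This is a genuine, small cost of the change. It does not justify counting off-drug days for everyone, since days on study drug and reasons for discontinuation appear in the same summary.

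A reader might also infer that many early stoppers would fall under the protocol's 80% mark, with consequences for the analysis. Arithmetically, a fully adherent subject scores under 80% whenever g exceeds I/4. But Protocol 6.4 gives "multiple missed doses resulting in <80% overall compliance at any point in the trial" as an example to guide the site's decision on whether a subject should continue. The SAP does not apply it to the 4.1.14 figure.

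**Conclusion.** The point holds as a minor definitional fault. As written, the rule can charge off-drug days as missed tablets. For a fully adherent Day 60 stopper, the understatement runs from nothing at a zero gap, through about 10 points at 7 days, to about 32 points at 28 days. Between arms that differ by 20 points in dropout, the artefact is 0 to about 6 points, about 2 at a 7-day gap. These sizes rest on assumed gaps, an assumed common stopping day and an assumed dropout difference.

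Two stronger readings are tempting and not supported. One is that early stoppers will necessarily look non-compliant; that depends on a gap the documents do not give. The other is that a particular arm will look worse; the documents give only an overall dropout rate, so which arm loses more subjects is unknown. Compliance defines no analysis population in SAP 5.2 and enters no efficacy model, test or sensitivity analysis.

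**What to change.** In SAP 4.1.14, replace days on study with days on IMP and refer to Section 4.1.6. The change is one phrase and needs no new data or definition. The price is that tablets skipped between an unreported last dose and the termination visit would no longer count as non-compliance. Days on study drug and reasons for discontinuation, already planned in SAP 5.8, show early stopping.

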The sponsor has a legal responsibility to notify both the local regulatory authority and other regulatory agencies about the safety of a trial intervention under clinical investigation. The sponsor will comply with country-specific regulatory requirements relating to safety reporting to the regulatory authority, IRBs/IECs, and investigators.

Investigator safety reports must be prepared for suspected unexpected serious adverse reactions (SUSAR) according to local regulatory requirements and sponsor policy and forwarded to investigators as necessary.

An investigator who receives an investigator safety report describing an SAE/AESI or other specific safety information (eg, summary or listing of SAEs/AESI) from the sponsor will review and then file it along with the Investigator's Brochure and will notify the IRB/IEC, if appropriate, according to local requirements.

8.4.5 *Pregnancy*

Details of all pregnancies in female subjects or in female partners of male subjects will be collected after the start of trial intervention and until 4 weeks after the last dose.

If a pregnancy is reported, the investigator should inform the sponsor within 24 hours of learning of the pregnancy and should follow the procedures outlined in [Section 10.4](#) (Appendix 4).

Abnormal pregnancy outcomes (eg, spontaneous abortion, fetal death, stillbirth, congenital anomalies, ectopic pregnancy) are considered SAEs.

8.4.6 *Adverse Events of Special Interest*

8.4.6.1 *Adverse Events Potentially Related to Abuse*

A key objective of the Abuse Potential Monitoring Plan (APMP) is to monitor for instances of abuse or diversion of the trial medication and other psychoactive substances.

In addition to monitoring for irregularities in medication handling, AEs that may be suggestive of a developing abuse issue will also receive special attention. As part of the APMP, medication handling irregularities (MHIs) must be reported, and AEs related to abuse potential and AEs involving MHIs must be reported as events subject to additional monitoring (ESAM), with detailed narratives.

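### Compliance credits every tablet in a kit that has no return data and is not recorded as lost, with no limit at the last-dose date, so it can exceed 100%

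*SAP*

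**What the plan says.** SAP 4.1.14 takes compliance from site records: "evaluation of compliance will be based on the site assessment of compliance as recorded on the DRUG ACCOUNTABILITY eCRF". The percentage is the number of tablets taken, "relative to the total expected number of tablets based on days on study". SAP 4.1.5 defines that period: "Days on Study is the number of days from Day 1 to the date of study completion or early termination". SAP 1.3.2 gives the daily number: "All subjects will take 3 tablets once daily of IMP throughout the Treatment Period".

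Where tablets are not accounted for, SAP 4.1.14 has three branches:

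- A lost kit with return information uses that information.
- A lost kit without it: "If a kit was lost and no return information was available, it is assumed that the tablets were not taken for the compliance calculation".
- A kit that is not lost and has no return information: "If return information is not available and the kit was not lost, it is assumed that the tablets were taken for the compliance calculation".

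The third branch has no upper limit and makes no use of the date of last dose. That date is available, because SAP 4.1.6 counts days on IMP from Day 1 "to the date of last dose of IMP as recorded on the EXPOSURE eCRF". SAP 4.1.14 does not say how values above 100% are handled. SAP 5.8 summarises compliance by treatment group in the FAS, alongside days on study drug and reasons for stopping.

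**The concern.** Two kits that never came back are treated in opposite ways, depending only on whether the site recorded a loss. One adds nothing to the numerator and the other adds all of its tablets. The SAP gives no reason for the difference.

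The full credit also ignores information that the SAP uses elsewhere. A subject's last dose may be recorded on the day a kit was dispensed, and compliance would still count that whole kit as swallowed afterwards. Days on drug and compliance, which SAP 5.8 reports together, would then contradict each other for that subject.

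At stake is the accuracy of a descriptive table. Compliance would be too high in the subjects whose drug-taking is least known. If kits without return data were more common in one arm, the comparison of compliance between arms would be distorted.

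**Working it through.** The documents state no compliance figure to reproduce, so the check applies the SAP 4.1.14 definition to a worked case.

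**Inputs from the documents**

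- 3 tablets per day (SAP 1.3.2).
- Denominator: 3 × days on study (SAP 4.1.14 and 4.1.5), with Day 1 counted as the first day.
- Visits at Days 98, 126 and 154 (schedule of assessments).
- Clinic visits follow that day's dose, taken at home (Protocol 4.1.2), so a kit dispensed on Day 98 serves Day 99 onward.

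**Assumptions, because the documents do not give them**

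- The kit holds exactly enough for the interval to the next visit: 3 × (126 − 98) = 84 tablets.
- The subject took every tablet up to Day 98 (3 × 98 = 294), then none.
- The kit has no return data and is not recorded as lost.
- The early-termination date is varied.

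**Result.** Tablets counted as taken under the SAP rule: 294 + 84 = 378. With no credit for the kit: 294.

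| Early termination dated | Expected tablets | SAP rule | No credit for the kit |
|---|---|---|---|
| Day 98 | 3 × 98 = 294 | 378/294 = 128.6% | 294/294 = 100.0% |
| Day 126 | 3 × 126 = 378 | 378/378 = 100.0% | 294/378 = 77.8% |
| Day 154 | 3 × 154 = 462 | 378/462 = 81.8% | 294/462 = 63.6% |

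**Sensitivity to the assumptions**

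- Three spare days in the kit (93 tablets), termination Day 126: (294 + 93)/378 = 102.4%.
- Prior adherence of 70%: 0.7 × 294 = 205.8 tablets. Then (205.8 + 84)/294 = 98.6% for termination on Day 98, and 289.8/378 = 76.7% for Day 126.
- Stopping after the Day 14 dispensing, with 3 × (35 − 14) = 63 tablets and 3 × 14 = 42 taken before: 105/42 = 250% for termination on Day 14. For Day 35 it is 105/105 = 100%, against 42/105 = 40.0% without credit.

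**Effect of a cap at the recorded last dose** (kit dispensed Day 98, termination Day 126)

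- Last dose Day 98: credit 3 × (98 − 98) = 0, giving 294/378 = 77.8%.
- Last dose Day 110: credit 3 × (110 − 98) = 36, giving (294 + 36)/378 = 87.3%.

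The cap gives credit for days on which the subject is recorded as dosed, and no more.

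**The case against.** The strongest defence is that neither imputation is clearly right. Some subjects take their tablets and fail to bring back the blister cards, and counting those tablets as not taken would understate compliance. That stands, and it is why the remedy should be a cap and not a switch to zero. The cap leans on the last-dose date, which may itself be uncertain for subjects lost to follow-up. That also stands.

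The number of kits affected may be small. Anyone who discontinues early is due the Week 27 assessments, which include a compliance check, and subjects are told to bring used and unused cards to each visit (Protocol 6.4). The case therefore mainly concerns subjects with no termination visit, and the documents do not let that number be estimated.

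Four stronger readings are tempting, and the documents do not support them.

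- A reader might infer that every unreturned kit counts as taken. It does not: the lost-kit branch goes the other way, and the documents do not say how a vanished subject's kit would be coded.
- A reader might infer that such a subject always scores as fully compliant. Exactly 100% needs full prior adherence, no spare tablets and termination dated at the next visit. Other assumptions give values above or below it.
- A reader might infer that the rule carries subjects past the 80% mark in Protocol 6.4. That mark prompts the site to consider discontinuing a subject; it is not an analysis threshold. In the example the subject took every tablet until stopping, and the 77.8% arises because the denominator runs over days on study and not days on drug.
- A reader might infer that diversion is concealed. The compliance figure would not show it, but it is not the tool for that. Under the monitoring plan in Protocol 8.4.6.1, "medication handling irregularities (MHIs) must be reported, and AEs related to abuse potential" and those involving MHIs are reported for additional monitoring, with narratives. SAP 5.14.1 summarises AEs involving MHIs separately. The monitoring plan's details are in another document, so it cannot be said that unreturned kits escape it.

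**Conclusion.** The point holds as a minor one. As written, the third branch of SAP 4.1.14 can count tablets as taken after the recorded last dose and can produce values above 100%. Relative to giving no credit for the kit, it never lowers the figure and usually raises it. In the worked case the excess is 28.6 percentage points for termination on Day 98 (128.6% against 100.0%) and 22.2 points for Day 126 (100.0% against 77.8%). These sizes rest on the assumed 84-tablet kit, full prior adherence and the chosen termination date. The direction does not.

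The consequence stays within the descriptive compliance summary of SAP 5.8. No population in SAP 5.2 is defined by compliance, and the efficacy models in SAP 5.9 and 5.10 do not use it. Nothing here shows that the arms differ in kits without return data.

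**What to change.** Replace the third branch of SAP 4.1.14. For a kit that is not lost and has no return information, credit at most 3 tablets per day from dispensing to the earlier of the next visit and the last-dose date on the EXPOSURE eCRF. Class the remaining tablets as unaccounted for, neither taken nor returned. Add to the SAP 5.8 summary the number of such kits, and of subjects with at least one, by treatment group. State how any value still above 100% is shown, since spare tablets or early visits could produce one by other routes.

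The cost is a short SAP edit and a small programming change, with no new data collection. Reported compliance will be slightly lower, and for subjects lost to follow-up the credited number will be only as reliable as their recorded last-dose date.
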